16. BASELINE VISIT

Assessments will be performed in accordance with Table 3. Insertion of the LTAD will occur at this visit.

16.1. Participants Randomised To the Long-Term Abdominal Drain (LTAD) (Group 1)

Rocket Medical LTADs will be used for this study (see Figure 2 Long-term abdominal drain in situ, courtesy of Rocket Medical plc). Participants attending for LTAD placement will have their travel costs reimbursed.

Figure 2. Long-term abdominal drain in situ

LTAD Insertion

While at most sites, LTAD insertion will be performed by interventional radiology (IR), this is not essential. Individuals inserting LTADs outside of IR should undergo a period of supervised practice in IR and be assessed as competent to perform the procedure independently. Once a LTAD has been inserted it is recommended that the ascites is drained to dryness in hospital with human albumin solution (20%) administered as per LVP protocol. (9, 64) This makes subsequent community management of ascites easier. It must be ensured by the medical and research teams that appropriate transport is available for the participant to travel safely to the hospital if they are allocated to the LTAD arm.

Routine checking of haemostatic function is not recommended prior to LVP (9, 64). However, inserting a LTAD is a more invasive procedure as it involves tunnelling. Therefore haemostatic function (INR and platelet count) will be checked within the preceding 7 +/- days of LTAD and corrected as per local trust guidance. In absence of local trust guidance please correct as below (see also Table 3)

INR < 1.5	no FFP will be administered
INR > 1.5	2 units of FFP administered
Platelet count > 50x10 ⁹	no platelets transfused
Platelet count < 50x10 ⁹	1-2 pools of platelets transfused

Technique of LTAD Insertion

The LTAD will be inserted with ultrasound guidance after informed consent has been received. Technique for insertion has been described previously. (45)

The insertion technique is a combination of tunnelled and Seldinger technique. After confirming the site for insertion with the help of ultrasound, local anaesthetic will be administered. A small incision is made where the catheter will enter the abdominal cavity. A Seldinger needle will be inserted through the incision into the peritoneal cavity and a guide wire is passed through the Seldinger needle which will then be removed.

A second incision will be made approximately 5cm away from the 1st, where the catheter will exit the tunnel.

The catheter will be tunnelled or threaded from the 2nd (exit site) incision to the 1st incision site with the tunneller, making sure the cuff is close to the 1st incision site.

The split sheath dilator will be then passed over the guide wire, the inner dilator and guide wire removed leaving the split sheath in situ.

The tunneller is removed from the catheter, which is then passed through the split sheath, separating the split sheath ensuring that all of the catheter is in the peritoneum.

The last of the split sheath is then removed.

REDUCe 2 protocol v2 20.06.22
The catheter is then adjusted along the tunnel, so the cuff moves towards the exit site. This will ensure that any possible kinks are removed from the catheter.

Avoiding the catheter, both incision sites will be sutured.

Use of Human Albumin Solution

Human Albumin Solution will not be administered to the LTAD group as outpatients.

Patients who remain symptomatic from ascites, despite drainage of 5L/week in the community should undergo supplementary LVP in hospital (via the LTAD) as required, with Human Albumin Solution replacement as per LVP protocol (9,64). In patients who recurrently require volumes higher than 5L drained off per week (e.g. 2 or more LVP in addition to 5L/week community drainage), higher volume community LTAD drainages can be considered on a **case-by-case basis**, in discussion with the named Principal Investigator/community teams

Ascitic fluid analysis

Routine ascitic fluid analysis in the LVP group will be performed at each drainage as is currently standard of care. In the LTAD group, routine ascitic fluid analysis will not be performed due to the likelihood of growing skin contaminants (80), the clinical significance of which remains uncertain. In those with a LTAD, ascitic fluid analysis will **ONLY** be performed if there is clinical suspicion for peritonitis: fever, abdominal pain, increased white cell count, worsening hepatic decompensation or renal function. In such instances the ascitic fluid sample will be taken for analysis from both the LTAD as well as via a separate ascitic tap. Peritionitis will be diagnosed if ascitic fluid neutrophil count is > 250/mm³, and or ascitic fluid white cell count is >500/mm³ and or if ascitic fluid culture is positive. (9, 64) Peritonitis will be treated as per current guidelines. (9, 64) Development of peritonitis will not necessarily mandate LTAD removal. This needs to be decided on a **case-by-case basis** after discussion between site teams and the CI.

LTAD (Group 1) post drain insertion care (also see Figure 1)

- The research team will explain to the patient and informal caregivers how the LTAD will be used and provide them with the drainage kit, which will include at least two weeks supply of drainage bags. The Research teams will provide patients with the LTAD manufacturer information sheet and discharge letter, the latter also being sent to the GP and community nursing team. The discharge letter will state that patients have been discharged with a LTAD. LTAD manufacturer details are included in the discharge letter. An additional community nurse referral will be sent to the community teams with basic instructions on LTAD management.
- The research team will also contact the appropriate lead community nurse to update them. This will ensure that home visits can be organised by the community team to

perform recurrent drainage and arrange necessary disposal of clinical waste. The research team will also inform the LTAD manufacturer so that they can organise additional bespoke training and support for participants/informal caregivers if needed and ensure supply of drainage bags

• The patient and community teams will be provided with the contact number for the research team. The patients will also be provided with written information describing LTAD management should they be admitted to hospital out of hours so that clinical teams are aware.

Community Management of LTAD

- The community nurses will visit patients at their usual residence to carry out ascites drainage as clinically indicated but drainage episodes should be limited to a maximum of three times a week. If additional training is required, the community nursing teams should contact the LTAD manufacturer as stated above. The amount to be drained will be dependent on clinical need, but would usually be 1-2L at a time with a maximum of 5L/week. Each time drainage is performed it will be recorded by the community nurses in a drainage diary which will be kept in the patient's usual place of residence. This drainage diary data will be collected by the research team members during fortnightly home visits and entered into the electronic Case Report Form (eCRF) by a member of the research team.
- Additional drainage bags will be delivered to patients by the research team during the fortnightly home visits. The drainage bags will be disposed of in the usual way by the council as per standard arrangements in that region.
- The contact telephone number for the research team to be used "in hours" (9am-5pm) during week days will be provided to community teams. Out of hours, patients or community healthcare professionals should contact the out-of-hours GP service or the patients should attend Accident and Emergency (A&E) for emergency trial related problems.
- The community nurses will perform risk assessments during their home visits as per their usual practice and inform the research team of any concerns that have been identified as regards
 - Drain leakage or blockage
 - Cellulitis at the drain site
 - Abdominal pain not settling with usual analgesia i.e. suspicion of peritonitis
 - Anything else which in the opinion of the community nurse is directly related to the LTAD and requires hospitalisation

- Community nurses will train informal caregivers if they wish to perform drainage. Though caregivers can assist with drainage, the drainage diary will still be completed by the community nurses
- Drainage of about 5L/week may not be sufficient for a small percentage of patients. In such instances patients can be admitted for supplementary LVP in hospital. This can be done via the LTAD (using specific adaptors). HAS will be administered as per LVP protocol. There will no need to take routine ascitic fluid samples from the LTAD and or do a routine diagnostic ascitic tap, unless suspicion for peritonitis. If patients are requiring frequent admission to hospital for supplementary LVP, then higher volume community LTAD drainage can be considered **on a case-by-case basis**, after discussion with the site PI, CI and community teams
- If a participant dies, the LTAD will be left in situ as per the usual practice. The community nursing team who will also follow standard procedures with regards to informing the undertakers of the presence of the LTAD.

Integrated Working Between Hospital and Community Teams

The success to implementing LTAD will be integrated working between hospital Gastroenterology/Hepatology, the community nursing teams (both the ones doing the drainage and the palliative teams), GPs and the patients/informal caregivers. Funding will be made available for sites to arrange up to two meeting with community teams to ensure engagement and collaboration. It can be difficult for HCP involved in the care of any patient near the end of life, especially in a cohort when death usually occurs in hospital. Research teams should be available to debrief community staff if needed.

For a summary of post-drain care, see Figure 1. Participant Flow Chart. A community standard operating procedure (SOP) will also be made available to all study sites.

16.2. Insertion Of Large Volume Paracentesis Drain (LVP), Group 2

At baseline participants randomised to the LVP group will undergo insertion in-line with standard of care. LVP involves insertion of a temporary drain by the usual medical team, usually drainage of 5-10 litres of ascites and use of intravenous (IV) human albumin solution (about 10 gms of albumin per 1-2L of fluid drained) (9, 64). If the total volume of fluid to be removed is < 5 litres then there will be no need to administer IV albumin. During LVP patients have routine bloods done in line with Table 3 Schedule of Assessments. A sample of ascites is sent at LVP, as per usual standard of care for white cell and neutrophil cell count and culture

To mitigate against research home visits impacting HRQoL in group 2 and thus diluting effects between the two groups, a SOP for the research home visits has been developed. The SOP

will promote standardisation of all the researcher visits to ensure they are limited to research tasks.

16.3. Antibiotic Use

There are no evidence-based guidelines on use of prophylactic antibiotics in setting of LTADs. NICE, European and BSG guidelines (9,64,81) recommend prophylactic antibiotics if total ascitic fluid protein is <15g/L. However, recent studies suggest that ascitic fluid protein may not predict peritonitis risk. (82-83) As already stated, peritonitis risk is more than two-fold higher when LTADs are inserted in patients with cirrhosis compared to those with malignant ascites. (38,44) Additionally, PPI feedback indicates that avoiding hospitalisation is the overarching goal for most patients. We would therefore recommend that all patients be offered prophylactic antibiotics as long as the LTAD remains in situ, especially if planned duration is for 3-months or longer. (80) Since this is a palliative cohort, the duration of antibiotic usage will in most patients be short-term in-keeping with overall life expectancy. Risk/benefits of prophylactic antibiotics should however be discussed with patients and their informal caregivers.

Both groups will:

- Receive ciprofloxacin 500 mg once a day (or an equivalent antibiotic depending on contraindications/local practice) for study duration
- Be referred to community palliative care and we will also record if the referral has been accepted and patient seen by the community palliative care teams
- Continue to receive all additional standard of care as clinically indicated. This includes symptomatic relief for pain (including use of opioids), shortness of breath, confusion (hepatic encephalopathy), jaundice and itching. Once deemed to have true refractory ascites there is little role for ongoing use of diuretics. (9, 64) As is current standard of care in patients with advanced cirrhosis, use of certain drugs (e.g. non-steroidal anti-inflammatory drugs (NSAIDS), aminoglyosides) will be avoided.

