9.5. Secondary endpoints/outcomes

- Cumulative peritonitis incidence in the LTAD and LVP groups
- Symptoms in LVP and LTAD groups assessed using the Ascites Q (74)
- Informal caregiver impact in LTAD and LVP groups assessed using the CRRS (75)

- Health resource utilisation in LTAD and LVP groups (modified AHCR (76-77) for community service use; hospital records for hospital service use using an inhouse designed questionnaire)
- Generic HRQoL and cost-utility analysis based on QALYs using EQ-5D-5L (78-79)
- Patient, caregiver and health care professional perceptions/perspectives of LTAD and LVP using qualitative methods

Table 2. Table of Endpoints / Outcomes

Objectives	Outcome measure	Timepoint(s) of evaluation of this outcome measure (if applicable)
Primary		
To assess whether palliative LTADs result in better health related quality of life (HRQoL) compared to LVP in patients with refractory ascites due to advanced cirrhosis. Secondary	Liver specific HRQoL assessed at 3 months with the SFLDQoL questionnaire	To be assessed at baseline and four weekly
To assess impact of LTADs and LVP on:		
Infections (especially peritonitis)	Cumulative peritonitis incidence in the LTAD and LVP groups	To be assessed at 3 months
Symptoms	Symptoms in LVP and LTAD groups assessed using Ascites Q	To be assessed at baseline and fortnightly for 3 months
Caregiver workload	Informal caregiver impact in LTAD and LVP groups assessed using CRRS	To be assessed at baseline and four weekly for 3 months

Health resource utilization	Health resource utilisation in LTAD and LVP groups: community service use (modified AHCR) and hospital records for hospital service use (inhouse designed questionnaire)	To be assessed at baseline and fortnightly, hospital service use at 3 months
	Generic HRQoL and cost-utility analysis based on QALYs using EQ-5D-5L	To be assessed at baseline and fortnightly
Explore perceptions of LTADs and LVP by patients, informal caregivers and healthcare professionals with qualitative interviews.	Patient, caregiver and health care professional perceptions/perspectives of LTAD and LVP using qualitative methods	Interviews (optional) to be conducted throughout the trial

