13. STUDY PROCEDURES

13.1. Schedule of Assessments

Table 3. Schedule of Assessments

		1		1		1	1	1	1
	Screening	Telephone call	Baseline / WO (7 +/- 3 days post screening)	W2 (+/- 3 days)	× W4 (+/- 3 days)	WG (+/- 3 days)	W8 (+/- 3 days)	W10 (+/- 3 days)	W12 (+/- 3 days)
Perform capacity check using capacity checklist.	X		x	X	X	X	X	Х	X
England sites : If patient loses capacity during study, approach Consultee									
Scotland sites : Capacity to be checked at start of study only.									
Informed Consent	Х								
(Informed consent can be given prior to the screening visit but must be confirmed at the screening visit)									
Demographics	X								
Medical History	x		x						
Routine clinical blood	X		X ¹	Х	Х	Х	Х	Х	Х
(Haemoglobin, white cell count, Platelets, APPT, INR/PT, Bilirubin, ALT, Alkaline phosphatase, Total protein, Albumin, Sodium, Potassium, Urea, Creatinine, eGFR, C reactive protein)									

Pregnancy test if child bearing age	X								
Diagnostic ascitic tap (white cell count, neutrophil count and culture)	X		X ¹	X ²					
Eligibility check (inclusion/exclusion)	X		×						
Vital signs	Х		Х	X	Х	X	X	X	Х
(Temperature, blood pressure and pulse)									
(Height and weight at baseline only)									
Liver disease scores (CPS/MELD/UKELD)	x		X	X	X	X	X	X	X
Liver disease assessment and history (includes hepatic encephalopathy, variceal bleeding, ascites and hepatocellular cancer	x		X	x	x	X	X	X	X
Alcohol and substance use assessment (self -reported)	Х		Х	Х	X	X	X	Х	X
Assessment of transport methods available to patient (in case the participant is to travel for LTAD insertion)	X								
Randomisation			Х						
(Can be done up to 10 days prior to the baseline visit)									
Notification of Randomisation		X							
telephone call									
(If randomisation is done prior to baseline visit)									
	1								

Optional Research blood sample 20ml	X						
(10ml for serum, 10ml for whole blood. To be frozen at -80°C for analysis at end of study)							
LTAD/LVP insertion ³	X ³						
Prophylactic antibiotics for both LTAD and LVP groups after discussing risks/benefits	X	X	X	X	X	X	X
Referral to palliative care for both LTAD and LVP groups	X						
LTAD (group 1) research team member to collect drainage data collated by community nurses, also assess LTAD and ask about abdominal pain	X	X	X	X	X	X	X
LVP (group 2) drainage assessment to be collected from medical records.	X	X	X	X	X	X	X
Adverse event review	X	X	X	X	X	X	X

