22.1. Assessing Relatedness of AE/SAEs

AE/SAEs will primarily be assessed for relatedness to the study interventions at the site by the Principal Investigator, or an investigator delegated to do so. Unrelated events will include but are not limited to the following:

- Hepatic encephalopathy
- Gastrointestinal bleeding related to peptic ulceration, hypertensive portal gastropathy or varices
- Liver cancer and or its treatment
- Complications of gastroscopy (perforation, bleeding)
- Complications of drug treatment for cirrhosis (lactulose, beta blockers, terlipressin, antibiotics, diuretics)
- Death related to the liver disease- will include death from liver failure, multiorgan failure, hepatorenal syndrome, variceal bleeding and sepsis

Unrelated events will be recorded in the eCRF but not reported to BSCTU, Sponsor or the REC.

If an event is considered to be related to the study interventions then they will be classified as an Adverse Reaction (AR) or a Serious Adverse Reaction (SAR) and will be assessed for Expectedness, as below.

Any potential SARs are to be recorded on the eCRF *and* reported to the BSCTU via email to [contact] immediately when sites become aware of the event, and at least within 24 hours.

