32. POST STUDY CARE

All research participants will continue to receive routine medical care as clinically indicated whether in the community, primary care or hospital setting. While participating in this trial, for no individual will routine clinical care be modified or denied. At the end of the trial, all participants will continue to be assessed by their usual medical care team. Those allocated to the LTAD arm will have the option, if they so wish, to continue with the LTAD under supervision of their usual Gastroenterologist/Hepatologist. If they elect to retain the LTADs, drainage bags will be provided by their GPs. If they elect to have the LTAD removed this will be done in hospital under local anaesthetic and they will revert back to hospital drainage. Those in the control arm (LVP group) will also continue as such. However, if LTAD is deemed to be beneficial, each site have the option to offer it to the control group outside of a trial setting.

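### Section 16.3 gives two prophylactic-antibiotic rules that differ on offer versus receipt and on stopping point, and section 22.1 pre-lists antibiotic complications as unrelated

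*Protocol*

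**What the plan says.** Section 16.3 argues for prophylaxis partly from the higher peritonitis risk with LTADs in cirrhosis, and concludes: "We would therefore recommend that all patients be offered prophylactic antibiotics as long as the LTAD remains in situ". It adds: "Risk/benefits of prophylactic antibiotics should however be discussed with patients and their informal caregivers". A list of what both groups will have then begins: "Receive ciprofloxacin 500 mg once a day (or an equivalent antibiotic depending on contraindications/local practice) for study duration".

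The schedule of assessments (section 13.1, Table 3) has its own line, marked at baseline and at the follow-up visits: "Prophylactic antibiotics for both LTAD and LVP groups after discussing risks/benefits". The same table contains a concomitant medication review.

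Section 22.1 lists events that are to be treated as unrelated to the study interventions. One entry is "Complications of drug treatment for cirrhosis (lactulose, beta blockers, terlipressin, antibiotics, diuretics". The consequence is stated there: "Unrelated events will be recorded in the eCRF but not reported to BSCTU, Sponsor or the REC".

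The outcome most exposed to prophylaxis is the first secondary outcome in section 9.5: "Cumulative peritonitis incidence in the LTAD and LVP groups". Under section 15.4 only the trial statistician is blinded.

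**The concern.** Prophylaxis is a co-intervention that acts directly on peritonitis, and section 8.3 names ascitic infection as the main worry about LTADs in cirrhosis. The comparison is easiest to interpret when prophylaxis is delivered alike in both arms, or when any difference is known. Two rules in one section, one of them timed by a device that only one arm has, leave sites to choose between them. Site staff know the allocation, so the choice can differ by arm. A site also cannot tell whether a participant who declines, or who stops when the drain is removed, has followed the protocol or deviated from it.

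The second matter is safety reporting. Complications of a drug that the protocol directs in both arms are classed as unrelated before anyone has looked at the case. The route for serious adverse reactions depends on relatedness, so such a reaction does not enter it.

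**Working it through.** The plan gives no figure on this point, and the primary sample size (93 per arm analysed, 310 randomised) does not enter. The check is mainly a comparison of the texts.

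**1. The two rules, case by case** (study period taken as the 12 weeks of follow-up)

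| Participant | Offer, while the drain is in place | Receipt, whole study period |
|---|---|---|
| LTAD, drain kept to week 12 | Offered, to week 12 | Given, to week 12 |
| LTAD, drain out before week 12 | Offered, ends at removal | Given, to week 12 |
| LVP | Included in the offer, but no end point defined | Given, to week 12 |
| Either arm, declines after discussion | Consistent with an offer | Not addressed |

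The rules agree fully only in the first row. The second row is foreseeable: Table 6 has a stop/go criterion on the percentage of LTADs removed because of peritonitis. Table 3 names both groups and requires a discussion, but does not settle the stopping point.

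**2. Recording**

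The list in section 16.3 commits to recording whether the palliative care referral was accepted and the patient seen. It makes no such commitment for the antibiotic. The medication review in Table 3 could capture it.

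**3. Safety route**

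- Section 22.1: antibiotic complications are unrelated, so they are recorded in the eCRF and not reported onward.
- Table 4: a serious adverse reaction must be attributed to one of the study treatments.
- Section 22.2: no antibiotic reaction is on the expected list.
- Section 5.1: the DSMC monitors adverse events.

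The data therefore exist and are open to periodic review. What is missing is case-by-case assessment and individual reporting to the trials unit, sponsor and ethics committee.

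**4. Illustration of size (every input assumed)**

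Assume no true device effect, peritonitis risk p0 without prophylaxis, prophylaxis risk ratio RR, and uptake u in an arm.

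- Risk in an arm = p0 × [1 − u × (1 − RR)]
- Spurious difference = p0 × (1 − RR) × (u in LTAD − u in LVP)

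Take p0 from 0.11 to 0.20, RR from 0.3 to 0.7, and LTAD uptake of 0.90.

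- LVP uptake 0.70: from 0.11 × 0.3 × 0.2 = 0.0066 to 0.20 × 0.7 × 0.2 = 0.028, that is 0.7 to 2.8 percentage points.
- LVP uptake 0.50: from 0.11 × 0.3 × 0.4 = 0.0132 to 0.20 × 0.7 × 0.4 = 0.056, that is 1.3 to 5.6 points.
- Equal uptake: 0.

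The feasibility trial showed 6% against 11%, a gap of 5 points. With 36 randomised, about 18 per arm, that is roughly one event against two (0.06 × 18 ≈ 1; 0.11 × 18 ≈ 2), so it is a weak yardstick.

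The sign follows the uptake difference. Fuller use in the LTAD arm would favour LTAD. Stopping at early drain removal would push the other way.

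**The case against.** The strongest reply is that the intent is plain. The offer is to all patients, the list in section 16.3 is addressed to both groups, and Table 3 names both. The sentence about the drain can be read as rationale, and a protocol-directed drug that a patient may decline is compatible with a discussion of risks and benefits. This disposes of one tempting inference, that LVP patients would be offered nothing. It does not supply a stopping point when a drain comes out early, nor say which of the two statements governs.

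Other stronger readings also go too far:

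- A reader might infer that the LTAD arm will in fact be treated more completely and its infection risk understated. The documents give no uptake figures, and section 8.3 reports that both groups in the feasibility trial received prophylaxis throughout. Unequal uptake is a possibility, not a finding.
- A reader might infer that antibiotic harms would be invisible to oversight. They would not: they enter an eCRF provided by the trials unit and checked by its data manager (section 26.2), and the DSMC monitors adverse events.
- A reader might see a conflict with section 32, which says that "for no individual will routine clinical care be modified or denied". That is a general assurance about access to care. Section 16.3 says guidelines recommend prophylaxis when ascitic protein is below 15 g/L, not exclusively then, and goes on to cite studies questioning that predictor.

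It can also be argued that relatedness in section 22.1 means relatedness to LTAD or LVP, and that antibiotics are background care in both arms. The entry does refer to drug treatment for cirrhosis in general and does not name the trial prophylaxis. But its wording covers it, and section 16.3 directs that prophylaxis as part of the study. The ambiguity stands.

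**Conclusion.** The point holds as an inconsistency in the text plus a reporting exclusion. Section 16.3 contains two rules that disagree on offer versus receipt and on duration, and Table 3 does not resolve them. Section 22.1 takes serious reactions to protocol-directed prophylaxis out of case-by-case assessment and individual reporting, although they are still recorded and adverse events are monitored by the DSMC.

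The effect on the peritonitis comparison is possible, but neither its size nor its direction can be computed from the documents. The ranges of 0.7 to 2.8 and 1.3 to 5.6 percentage points rest wholly on assumed baseline risk, prophylaxis effect and uptake, and serve only to show that an uptake gap could matter on the scale of this outcome. The primary sample size is not affected. The correction is worth making because it is cheap and concerns a safety outcome central to the trial.

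**What to change.** 1. Reconcile section 16.3 and Table 3 into one prophylaxis rule, used identically in both places and defined for both arms. It should make clear whether prophylaxis is offered or given, when it ends in each arm, what applies if an LTAD is removed before week 12, and whether declining is a deviation. The content of the rule is for the clinical team.
2. Use the existing concomitant medication review to record prophylaxis in both arms (offered, accepted, agent, days taken since the last visit), and report uptake by arm beside the peritonitis result.
3. In section 22.1, exclude protocol-directed prophylactic antibiotics from the pre-listed unrelated events. Say that serious reactions to them are assessed case by case and reported as for other serious adverse reactions, and align the study-treatment wording in Table 4 and the expectedness list in section 22.2 with this.

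The cost is protocol wording, a small addition to the eCRF and a few more safety reports. No extra visits are needed.
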